## Scoring Occurring at a Later Time (at CHLA or USC)

Dentist-Scoring. At CHLA, a dentist blinded to condition (RDE/SADE) will score the intraoral photographs using the Plaque Index. (See CRF 16: Quality of Care Recording Form). The rater will be a dental resident who has achieved both inter-rater and intra-rater reliability.

Researcher-Scoring. At USC, a researcher will code video-recordings of the child behavior during the cleaning using the training program developed by [name] and the study team during the R34 (it is not possible to blind to environment on video-recordings as the environment is obvious based on amount of ambient light in the room); this coder will achieve inter-rater reliability with [name] (Co-I) and will change once per year. A researcher blinded to environment (RDE/SADE) will score the EDA recordings using the BIOPAC program Acq*Knowledge;* this coder will achieve inter-rater reliability with [name] (Co-I) and will be responsible for EDA analyses for the entirety of the study (See CRFs 22-23: CDBRS & Scored EDA Forms).

### 9 ASSESSMENT OF SAFETY

## 9.1 Specification of Safety Parameters

Safety monitoring for this study will focus on unanticipated problems involving risks to participants, including unanticipated problems that meet the definition of a serious adverse event.

Some of the children who participate in this study may experience adverse events that are not related to study procedures, but are related to the participants' diagnosis of Autism Spectrum Disorders, and the treatment for these conditions. Such events will not be captured and reported for the study, as they will not meet the definition of an unanticipated problem.

# 9.1.1 Unanticipated Problems

The Office for Human Research Protections (OHRP) considers unanticipated problems involving risks to subjects or others to include, in general, any incident, experience, or outcome that meets **all** of the following criteria:

- unexpected in terms of nature, severity, or frequency given (a) the research procedures
  that are described in the protocol-related documents, such as the IRB-approved
  research protocol and informed consent document; and (b) the characteristics of the
  subject population being studied;
- related or possibly related to participation in the research ("possibly related" means there
  is a reasonable possibility that the incident, experience, or outcome may have been
  caused by the procedures involved in the research); and
- suggests that the research places subjects or others at a greater risk of harm (including physical, psychological, economic, or social harm) than was previously known or recognized.

### 9.1.2 Adverse Events

An adverse event is any untoward or unfavorable medical occurrence in a human subject, including any abnormal sign (for example, abnormal physical exam or laboratory finding), symptom, or disease, temporally associated with the subject's participation in the research, whether or not considered related to the subject's participation in the research. Adverse events related to participants' ASD diagnosis and related treatment will not be reported in this study, as these are not considered Unanticipated Problems. Adverse events, unless serious, will not be reported.

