- c) We will enact a sequential procedure, for each research participant undergoing the SADE that consists of: (1) prior to the treatment, explaining each component of the intervention (both through a social story and verbally) and getting the child's assent (when able); (2) requiring the research team to monitor any negative reactions to the SADE adaptations; and (3) having the dental assistant or dentist remove or minimize offending stimuli that emerge during the above steps (or terminate cleaning if necessary).
- d) The study will have a data safety monitoring committee (CSOC) which will review all adverse events in an effort to ensure the welfare of all research participants.
- e) During the time of the COVID-19 pandemic, participants are at a small risk of contracting the virus when they leave their home and come to CHLA. CHLA has launched extensive protective measures to prevent the spread of the novel coronavirus and keep patients, families and team members safe.

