# 9.5 Halting Rules

Safety findings that would temporarily suspend enrollment and/or study interventions until a safety review is convened include SAEs. A safety review will be conducted if there are a large number of SAE's overall, a large number of occurrences of a particular type of SAE, severe AEs/reactions, or increased frequency of events.

Subsequent review of serious, unexpected problems by the Medical Monitor, CSOC, IRB, the sponsor(s), or the relevant local regulatory authorities may also result in suspension of additional enrollment as well as further trial interventions.

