### 10 STUDY OVERSIGHT

In addition to the Pl's responsibility for oversight, study oversight will be under the direction of a Clinical Study Oversight Committee (CSOC) composed of members with expertise to oversee the study including expertise in autism spectrum disorders, occupational therapy, pediatric dentistry, and statistical analysis of clinical trials data. The CSOC will meet to review the clinical protocol before study recruitment begins, and then approximately annually to assess unanticipated problems, study conduct, and progress. If major concerns arise, more frequent meetings may be held. The CSOC will operate under the rules of an NIDCR-approved charter that will be approved at the organizational meeting of the CSOC. At this time, most data elements that the CSOC needs to assess will be clearly defined. The CSOC will provide recommendations to the NIDCR. In addition to the CSOC, an internal system for monitoring adverse events will be set up in conjunction with the study's database system. As per NIDCR guidelines, members of the CSOC will be appointed by NIDCR.

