# 16.3 Types of Data

Data collected will include descriptive data of the participants and outcome measure data. Descriptive data characterizing the participants will include questionnaire responses from parents and children. Outcome measure data will include questionnaire responses from children and dental professionals, oral health indices, physiological recordings from children, and video-recordings of children undergoing dental cleanings (See CRFs 5-23 for a list of all child-descriptor and outcome measures; see Appendix A for Schedule of Events).

As our intervention modifies the dental environment and does not change the traditional dental cleaning protocol, we will question parents and dental professionals regarding adverse events and serious adverse events as our safety data collection. This will occur prior to and following each dental visit, and information will be stored in the same secure Café database as our other data.

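### Section 9.1.2 keeps non-serious adverse events out of reporting, but the CSOC commitment in 2.2.1 and two of the four review grounds in 9.5 need them, and 9.2 and 16.3 disagree on whether they are collected

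*Combined protocol and SAP*

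**What the plan says.** Some sections of the protocol keep non-serious adverse events (AEs) out of the reporting system:

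- Section 9.1.2: "Adverse events, unless serious, will not be reported".
- Section 9.2: the investigator asks at each visit about UPs and about SAEs unrelated to autism. Staff record events that are reportable. The forms named are for UPs and SAEs. The visit instructions in section 7.3 likewise mention only UPs.
- Section 10: the CSOC meets "approximately annually to assess unanticipated problems, study conduct, and progress". Non-serious AEs are not named.

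Others assume that these events are collected or reviewed:

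- Section 2.2.1, among the precautions for the butterfly vest: "The study will have a data safety monitoring committee (CSOC) which will review all adverse events".
- Section 9.5, as grounds for a safety review after two grounds based on SAE counts: "severe AEs/reactions, or increased frequency of events".
- Section 16.3: "we will question parents and dental professionals regarding adverse events and serious adverse events as our safety data collection". This happens before and after each dental visit, and the answers go into the study database.
- Section 7.4: parents are told to contact the team about AEs as well as SAEs after Visit 4.
- Section 9.3.3 grades AEs as mild, moderate or severe. Section 16.1 requires the principal investigator to review AEs. Section 10 promises an in-house AE monitoring system linked to the database.

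**The concern.** The harms that section 2.2.1 anticipates are mostly non-serious: skin irritation from the electrode gel, fear of the electrodes, anxiety brought on by the vest, gingival bleeding and mild discomfort. The same section concedes that the vest in effect restrains the child, and it offers CSOC review of all AEs as one of the safeguards. If 9.1.2 and 9.2 are followed literally, the events that this safeguard is most likely to concern are not asked about, have no named form and are not reported.

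What is at stake is oversight. The CSOC could meet without seeing whether expected reactions are more frequent or more severe in the sensory adapted environment (SADE) than in the regular one (RDE), although one section says that it will see all of them. The primary analysis and the sample size are not affected.

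**Working it through.** There is no figure to reproduce: section 9.5 gives neither a threshold nor a reference rate. The check is a comparison of the passages.

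**Step 1. Count what section 9.5 needs.** Suspension is tied to SAEs: "Safety findings that would temporarily suspend enrollment and/or study interventions until a safety review is convened include SAEs". Four grounds for a safety review follow.

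| Ground in 9.5 | Data needed | Available under 9.1.2? |
|---|---|---|
| SAEs overall | SAEs | Yes |
| SAEs of one type | SAEs | Yes |
| Severe AEs or reactions | AEs graded by severity, serious or not | Only those that are also SAEs or UPs |
| Increased frequency of events | All events, on the natural reading | Only SAEs and UPs |

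The first two grounds, "a large number of SAE's overall, a large number of occurrences of a particular type of SAE", work as written, since section 9.4.2 has SAEs submitted within 24 or 72 hours. The other two, 2 of 4, are only partly supplied. The third is listed separately from the SAE grounds, and severity (9.3.3) is a different scale from seriousness (9.1.3). A reaction can therefore be severe without being serious.

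**Step 2. Test whether the UP route fills the gap.** Section 9.1.1 requires three things together: the event is unexpected in nature, severity or frequency given the protocol and the population; it is at least possibly related to the research; and it suggests greater risk than was recognised. A UP that is not serious goes to the IRB and NIDCR within 2 weeks (9.4.1), and the CSOC assesses UPs (section 10). A reaction clearly worse than those described could qualify. A reaction of a listed kind and ordinary severity usually fails the first test. Unexpected frequency could make it a UP, but that can be judged only if ordinary occurrences are recorded and counted.

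**Step 3. Follow one event through the plan.** Take a child with marked, non-serious distress in the vest, of the kind foreseen in 2.2.1.

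- *Asked about?* Not under 9.2; yes under 16.3.
- *Recorded?* 9.2 ties recording to reportability and names no form for it; 16.3 says the answer is stored.
- *Seen by the principal investigator?* Yes, under 16.1, if recorded.
- *Passed to the CSOC?* No stated route. Section 10 does not link the in-house system to the CSOC. The scheduled reports in 16.4 cover enrolment and child descriptors. Section 12.4 contains no AE tabulation.

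**Step 4. Compare the two descriptions of the CSOC's task.** The one in section 10 can be met under 9.1.2. The one in 2.2.1, a committee "which will review all adverse events in an effort to ensure the welfare of all research participants", cannot.

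**The case against.** The best reply is that section 9.1.2 concerns expedited reporting only, and that restricting this to SAEs and UPs is a reasonable choice in a study that section 12.3.1 describes as low risk. On that view AEs are still collected (16.3), monitored in-house (section 10) and reviewed by the principal investigator (16.1). Section 10 adds that most of the data elements the CSOC needs will be defined when its charter is approved. The charter, the manual of procedures and the case report forms are not in the text reviewed, so a listing for the CSOC may exist there.

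Much of this stands, and it rules out several stronger conclusions that a reader might draw:

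- *That neither the halting rule nor CSOC review can work.* Suspension, two of the four review grounds and the section 10 remit do not need non-serious AEs.
- *That no non-serious event can reach the CSOC or prompt a review.* Non-serious UPs can, including those unexpected in severity or frequency.
- *That a safety comparison of SADE with RDE is void by design.* No objective or hypothesis plans one. Distress, pain, EDA and the need for stabilization or sedation are measured in both environments as outcomes, and refusals of any element are documented (2.2.1).
- *That a certain number of events would go unseen.* The documents give no event rate for this trial, and the pilot, with 44 children, reported no AEs.

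The reply does not remove the conflict. Section 9.1.2 is worded without limit to expedited reports, 9.2 omits non-serious AEs from both enquiry and forms, and no section in the text carries them from the database or the principal investigator to the committee that is said to review them all.

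**Conclusion.** The point holds as an internal contradiction with a limited but real effect on safety oversight, and it should be corrected. Non-serious reactions of an already listed kind have no stated route to the CSOC. As a result, one of the two descriptions of the CSOC's task (2.2.1) cannot be honoured, two of the four review grounds in 9.5 are undercut, though not disabled, and 9.2 and 16.3 disagree on whether the events are elicited at all.

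This rests on three readings. The reporting exclusion in 9.1.2 is taken to cover routine as well as expedited reporting. The frequency ground in 9.5 is taken to include AEs; if it meant only SAEs and UPs, one of the four grounds would be affected instead of two. The charter, manual and forms are taken not to supply the missing route, which cannot be checked from the text.

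Timing also limits what can be gained. According to the COVID-19 note in section 7.3, all participants had completed Visits 1 to 3 and 25 second cleanings were outstanding. New recording can reach at most those 25 cleanings. Most of the benefit would come from tabulating answers already stored under 16.3, if they were collected as that section says.

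**What to change.** 1. Reconcile sections 2.2.1, 9.1.2, 9.2, 9.5, 10 and 16.3, so that they agree on which events are asked about, recorded, reported and reviewed, and by whom. In 9.1.2, separate expedited reporting from recording and periodic review.
2. State that AEs elicited under 16.3 are recorded with their severity grade (9.3.3) and the environment of the visit, and name the form in 9.2.
3. Give the CSOC a listing of these events by environment (SADE or RDE), covering answers already in the database and the remaining visits.
4. Keep expedited reporting for SAEs and UPs as it stands.

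Which events should prompt a review or a suspension is for the investigators and the CSOC to settle. The request here is that the sections agree and that the chosen rule has the data it needs.

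The cost is protocol wording, a little more data entry and one table in the CSOC report. The design, sample size and primary analysis do not change. If the stored answers turn out not to exist, because 9.2 was followed instead of 16.3, that should be stated to the CSOC, and the listing would cover only the remaining visits.

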### 9.1.3 Serious Adverse Events

A serious adverse event (SAE) is one that meets one or more of the following criteria:

- Results in death
- Is life-threatening (places the subject at immediate risk of death from the event as it occurred)

- Results in inpatient hospitalization or prolongation of existing hospitalization
- Results in a persistent or significant disability or incapacity
- Results in a congenital anomaly or birth defect
- An important medical event that may not result in death, be life threatening, or require
  hospitalization may be considered an SAE when, based upon appropriate medical
  judgment, the event may jeopardize the subject and may require medical or surgical
  intervention to prevent one of the outcomes listed in this definition.

Adverse Events related to participants' diagnosis of ASD will not be reported, as these are not considered Unanticipated Problems.

## 9.2 Time Period and Frequency for Event Assessment and Follow-Up

Unanticipated problems will be recorded in the data collection system throughout the study.

A trained research team member will record all reportable events with start dates occurring any time after informed consent is obtained until 30 days (for SAEs) after the last day of study participation. At each study visit, the investigator will inquire about the occurrence of UPs, and of SAEs not related to participants' diagnosis of ASD or related treatment, since the last visit. Events will be followed for outcome information until resolution or stabilization (See CRFs 27-29: Unanticipated Problem Form, Serious Adverse Event Form).

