One factor that may contribute to oral care challenges in children with ASD is sensory over-responsivity characterized by behavioral responses that are out of proportion to the type or amount of stimulation. These responses may include physical withdrawal, vocal outbursts, aggressive behaviors, tantrums, or attempts to block incoming stimulation. Although the mechanisms underlying sensory processing disorders are not fully understood, such problems are highly prevalent in the ASD population. Up to 95% of children with ASD demonstrate significantly different sensory behaviors than their TD counterparts, and 61% specifically exhibit tactile over-responsivity symptoms as evidenced by difficulty tolerating grooming and hygiene tasks.

Exacerbation of sensory over-responsivity in the dental office can result from exposure to bright lights, loud or high-pitched noises, reclining in the dental chair, repeated touch in and around the mouth, and the texture, taste, and smell of various oral care products. In a survey of 196 parents of children with ASD, up to 70% of parents reported that their child experienced difficulty with each of these sensory variables in the dental office, with the greatest difficulty being instruments in the mouth (70%). In this study, almost 50% of parents of children with ASD strongly agreed that their child's sensory over-responsivity made visits to the dentist more challenging. Additionally, children with ASD with sensory over-responsivity, compared to children with ASD without sensory over-responsivity, exhibited a significantly greater prevalence of oral care difficulties in the home and dental office. In focus groups that we conducted, parents reported reluctance to return to the dentist because of their child's negative experiences. For example, one parent stated that "The first time we took him to the dentist, when I heard him screaming for me from the front, I kind of understood how bad this was...there was like several people trying to restrain him. They had him in restraints and my wife [in the room with him] was in tears...because of that experience we were extremely hesitant to take him back."

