## 7.4 Final Study Visit

## Final Study Visit = Visit 4 (125-450 days)

This study's final visit will be the second dental cleaning visit at CHLA; there are no special procedures or evaluations (other than those noted in Visit 4 above) to be completed after the second dental cleaning.

Upon completion of the second dental cleaning, participants and parents will be informed that the study is complete and oral care will return to as it was prior to the study (e.g., continue recalls at CHLA every 6 months if CHLA client, or return to other dentist if not a CHLA client) with no further compensation or access to the adapted environment. Parents will again be given contact information of research team members in the case that they have any questions or want to contact the researchers (also located on the signed and dated copy of the consent form). Parents will be instructed to contact the research team if any AEs or SAEs occur following Visit 4. If appropriate, a member of the research team will follow-up via phone call to ensure that any AE/SAEs have been resolved. Individual participants will not be informed of study results.

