### 7.5 Withdrawal Visit

There will not be a withdrawal visit and no evaluations are specifically required for the final visit as the final visit is the second dental cleaning visit (Visit 4 above).

We will make every attempt to ensure that each child gets two dental cleanings, one in each condition (SADE and RDE). Missed appointments will be rescheduled, as many times as necessary up to eight months following the child's first dental cleaning (with participants receiving priority scheduling), extra reminders made, and compensation provided to cover transportation costs and time. If a child does not complete his/her second cleaning within eight

months of his/her first, we will assume that he/she has voluntarily withdrawn and will inform parents that their child is no longer eligible to obtain the second dental cleaning, nor is part of the study anymore. Parents will also be reminded that there will be no penalty or impact on CHLA quality of care as a result of withdrawing or dropping out of the study.

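### The 30-day SAE window after participation has no scheduled enquiry, and non-returners are assumed withdrawn with no safety question or reason recorded

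*Combined protocol and SAP*

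**What the plan says.** Section 9.2 sets the recording period for reportable events as "any time after informed consent is obtained until 30 days (for SAEs) after the last day of study participation". Its enquiry is tied to visits: "At each study visit, the investigator will inquire about the occurrence of UPs", and about unrelated-to-ASD SAEs, looking back to the previous visit. Section 16.3 adds that parents and dental professionals are questioned about AEs and SAEs. It says "This will occur prior to and following each dental visit" and gives no interval for the questioning afterwards.

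Section 7.4 states: "This study's final visit will be the second dental cleaning visit at CHLA". From then on the route is passive: "Parents will be instructed to contact the research team if any AEs or SAEs occur following Visit 4". The only call by the team is conditional and concerns resolution: "If appropriate, a member of the research team will follow-up via phone call to ensure that any AE/SAEs have been resolved".

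Section 7.5 provides no withdrawal visit. On a child whose second cleaning has not happened by the eight-month limit, it states: "we will assume that he/she has voluntarily withdrawn and will inform parents that their child is no longer eligible to obtain the second dental cleaning". Section 5.5 lists the same eight-month lapse as something for which the investigator may end participation. Section 12.4 plans a descriptive comparison of the two visit orders that includes the attrition rate.

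**The concern.** A collection window is only as good as the contact that closes it. Here the window runs 30 days past participation, but the last contact initiated by the study is a visit, or questioning around a visit that may take place on the same day. A serious event that starts after that reaches the record only if a parent volunteers it.

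Non-returners raise a second problem. Their families are told that they are out of the study, but the plan does not say that anyone asks about events or why they did not come back. The instruction to report later events is given at the end of the second cleaning, which these families never attend. It is also unclear when participation ends for them: at the first cleaning or at the eight-month limit.

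The introduction itself recognises that a bad dental visit can keep a family away; one parent said "because of that experience we were extremely hesitant to take him back". Section 2.2.1 lists vest-induced anxiety as a possible risk, though it judges that risk low. If some non-return reflects how the child took the visit, a default label of voluntary withdrawal removes the information that would show it.

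**Working it through.** **Sections side by side**

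- Window: to 30 days after the end of participation (9.2).
- Active enquiry: at study visits (9.2), and before and after each dental visit at an undefined interval (16.3).
- After Visit 4: parents report; the team phones if appropriate (7.4).
- After non-return: a contact is made to inform the parents, with no stated safety content (7.5).
- Status of non-return: voluntary withdrawal by assumption (7.5), or possible investigator termination (5.5).

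No entry is a scheduled contact that covers the 30 days.

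**Inputs for the size**

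- 220 recruited, 165 with complete data, stated loss 10% (5.3 Retention; 12.2).
- Pilot attrition 2% (12.2).
- 25 children awaiting Visit 4 at the COVID-19 stop (7.3).
- One cleaning in each environment per child (6.2).
- Order randomised in blocks within strata (5.4.1). The ratio is not stated, so I assume 1:1.
- I take all 220 as randomised and receiving a first cleaning.

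**The plan's own attrition figures**

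220 × 0.90 = 198, not 165. In the other direction, 165 / 0.90 = 183.3, so 184, not 220. The pair 165/220 implies a loss of 1 − 0.75 = 25%. That mismatch is a separate matter; here I use 10% and 25% as a range. The documents give no figure for exposures without a later enquiry.

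**Share of SADE exposures with no later study visit**

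Let n be the number randomised and d the loss between the two cleanings, equal in both orders.

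- SADE exposures = n/2 + (n/2)(1 − d) = (n/2)(2 − d).
- With no later visit: SADE-first children who are lost, (n/2)d, plus everyone who has SADE second, (n/2)(1 − d). The sum is n/2.
- Share = 1/(2 − d).

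| Loss d | Calculation | Share |
|---|---|---|
| 0% | 110/220 | 50.0% |
| 2% | 110/217.8 | 50.5% |
| 10% | 110/209 | 52.6% |
| 25/220 = 11.4% | 110/207.5 | 53.0% |
| 25% | 110/192.5 | 57.1% |

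If loss is unequal:

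- 10% lost from RDE-first only: (110 − 11)/(110 + 99) = 99/209 = 47.4%.
- 10% lost from SADE-first only: (11 + 110)/220 = 121/220 = 55.0%.

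**How much of this is non-return**

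SADE-first children who are lost make up 11/209 = 5.3% of exposures at 10% loss, and 27.5/192.5 = 14.3% at 25%. The rest (99/209 = 47.4%, or 82.5/192.5 = 42.9%) is simply that Visit 4 is last. Under equal loss the same formula holds for RDE.

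**The case against.** The strongest reply is that the reactions one would worry about happen in the chair and are recorded for every child, whether or not the child returns. The parent is present, refusals of components are documented and the team monitors negative reactions (2.2.1). Unanticipated problems are recorded at both cleanings (7.3). The whole cleaning is videotaped, and child and parent acceptance forms follow the SADE visit (8.1). All of this stands. A reader might infer that the post-SADE safety record contains only children who tolerated the visit; for in-visit reactions the documents do not support that.

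A reader might also infer that children lost after the first cleaning are never asked about events. Section 16.3 contradicts this, because parents are questioned after each dental visit. What is missing is an enquiry at a stated time later on. If the questioning in 16.3 is meant to extend beyond the same day, the gap narrows, but the text would have to say so.

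The parent's remark in the introduction concerns restraint at an ordinary dental visit, not SADE. It shows that a bad visit can lead to non-return, but not that SADE causes it. If anything it could point to loss after RDE, which would bring the share down to the 47.4% case.

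Proportion matters too. The plan calls the study low risk (12.3.1), the pilot reported no adverse events (2.2.1), and non-serious adverse events are not reported (9.1.2). Passive SAE reporting for a final 30 days can be defended. Unanticipated problems, however, can include psychological harm without being SAEs (9.1.1), so a later enquiry would not be confined to hospital-type events.

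The case report forms and the Manual of Procedures are not available here. A field for the reason for non-return may exist there, and contact attempts are logged on the Call Log Form (6.4).

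**Conclusion.** The point holds as a minor one. The protocol states a 30-day SAE window that no scheduled enquiry covers. It gives non-returners a default status without asking about events or reasons, leaves the end of their participation undefined, and describes their status differently in 5.5 and 7.5.

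About half of SADE exposures have no later study-visit enquiry: 50.0% to 57.1% with equal loss of 0% to 25%, and 47.4% or 55.0% if a 10% loss falls on one order only. These figures assume 1:1 order and that all 220 receive a first cleaning. They should not be read as over half of exposures going unasked because families drop out. Most of the share comes from Visit 4 being last, and it applies equally to RDE, so under equal loss it does not tilt the comparison. Nor can the difference between 220 and 165 be read as 55 children lost after a first cleaning. Complete data can also be missing because ASD was not confirmed before randomisation or because recordings were unusable.

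The more useful loss is in interpretation: without recorded reasons, the attrition comparison by order in 12.4 cannot separate intolerance of an environment from scheduling loss.

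**What to change.** 1. In 7.5, replace the assumption of voluntary withdrawal with a record. At the contact already made to inform parents, ask the 9.2 questions on unanticipated problems and SAEs and the reason for not returning, with reaction to the visit or environment as one option. Log both, and report reasons by the environment of the first cleaning alongside the 12.4 attrition comparison.
2. Define the last day of participation, including for non-returners. Send one enquiry 30 days after the last cleaning by the parent's preferred channel, logged on the Call Log Form. Section 7.3 says all children had completed Visits 1 to 3 and 25 still awaited Visit 4, so this can act prospectively on up to 25 children. For earlier children, disclose passive capture as a limitation.
3. Reconcile 5.5, 7.4, 7.5, 9.2 and 16.3 on the status of non-returners, the timing of questioning after a dental visit, and the route for later events. The eight-month limit itself need not change.

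The cost is a short amendment, a few added questions at an existing contact, up to 25 messages through existing channels, and possibly a few more events to record. No endpoint, sample size or clinical procedure changes.
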